6.7. Study drug regimens

Overview of drug regimens	
1-step AS-arm	2-step AS-arm

1-step parenteral AS
 
New injectable artesunate (Argesun) 60mg
 
Each vial of powder contains 60mg artesunate. Each ampoule of 6 ml solvent contains: sodium bicarbonate 8.4mg/ml; arginine 20mg/ml.
 
Guilin Pharma, Guangxi, China Artesunate 2.4 mg/kg STAT on admission, 12hrs, then daily. <20 kg children will get artesunate 3.0 mg/kg. Minimal 3 doses.
 
FOLLOWED BY
 
Oral artemisinin combination therapy x 3 days
	
Conventional 2-step parenteral AS
 
Conventional injectable artesunate (Artesun) 60mg
 
Each vial of powder contains 60 mg artesunate. Each ampoule of 1 ml solvent contains 50 mg sodium bicarbonate. Each ampoule of 5 ml diluent contains 45 mg sodium chloride.
 
Guilin Pharma, Guangxi, China Artesunate 2.4 mg/kg STAT on admission, 12hrs, then daily. <20 kg children will get artesunate 3.0 mg/kg. Minimal 3 doses.
 
FOLLOWED BY
 
Oral artemisinin combination therapy x 3 days

Patients will be treated with weight-based doses according to the schedule in Appendix 1.

The ACT used will be artemether-lumefantrine if available, given according to manufacturer's instructions. The ACT will be administered by study medical or nursing staff while the patients are hospitalised. Directly Observed Therapy (DOT) will be done if possible, but in all cases the first dose of ACT will be by DOT. During DOT, if the patient vomits within half an hour after intake of ACT, the full dose will be repeated. If vomiting occurs between half and one hour, half of the dose will be repeated. If vomiting occurs more than one hour after drug administration, no repeat dosing will be done. Repeat doses will be recorded on the CRF. If vomiting within 1 hour occurs more than one time, no repeat dosing is allowed. The patient will be treated at the discretion of the investigator.

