The most important reported side effect of artesunate is a rare severe allergic reaction (estimated risk approximately 1 in 3000 patients), which can present as an urticarial rash or more severe allergic symptoms, including hypotension, pruritus, oedema, and/or dyspnoea. More common minor side effects described in association with parenteral administration of artesunate include dizziness, light-headedness, rash, and taste alteration (metallic/ bitter taste). Nausea, vomiting, anorexia and diarrhoea have also been reported, however it is uncertain whether these are attributable to the drug or to the disease severe malaria.

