2.1.3. Secondary objectives and endpoints

1. To assess and compare *P. falciparum* parasite clearance rates of 1-step vs. conventional 2-step parenteral artesunate formulations.

Parasite clearance half-life and other parasite clearance parameters (PC50, PC90, 12-hour parasite reduction ratio) compared between 1-step vs. conventional 2-step parenteral artesunate formulations.

2. To assess and compare time from intravenous treatment to follow up treatment with oral drugs with 1-step vs. conventional 2-step parenteral artesunate formulations.

Time from start parenteral treatment to follow up treatment with an oral ACT (recovery to per os treatment) of 1-step vs. conventional 2-step parenteral artesunate formulations.

3. To assess and compare disease outcome parameters between 1-step vs. conventional parenteral artesunate formulations.

Fever clearance time (i.e. the time taken for the tympanic temperature to fall below 37.5 °C and remain there for at least 24 hours) of 1-step vs. conventional 2-step parenteral artesunate formulations.

4. To assess and compare adverse events between 1-step vs. conventional 2-step parenteral artesunate formulations

Incidence of adverse events and serious adverse events by study arms within the first 28 days.

STATISTICAL ANALYSIS PLAN

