3.4 Fever clearance and parasite clearance during treatment, by treatment allocation

Table 4 Clinical recovery*, fever clearance, and parasite clearance by study arm**

	1-STEP AS N=XXX	2-STEP AS N=XXX	Both groups N=XXX	P- value (2-sided)
Hours to fever clearance, mean (SD) (baseline to start of first 24h period <37.5C; temperature was recorded every 4 hours, until day 2, then 6 hourly)				
DRC	XX.X (X.X)	XX.X (X.X)	XX.X (X.X)	X.XXX
Tanzania	XX.X (X.X)	XX.X (X.X)	XX.X (X.X)	X.XXX
All study sites	XX.X (X.X)	XX.X (X.X)	XX.X (X.X)	X.XXX
Day 3 blood smear still positive, n/N (%)** (taking prior clearance or discharge as negative)				
DRC	XX/XXX (XX)	XX/XXX (XX)	XX/XXX (XX)	X.XXX
Tanzania	XX/XXX (XX)	XX/XXX (XX)	XX/XXX (XX)	X.XXX
All study sites	XX/XXX (XX)	XX/XXX (XX)	XX/XXX (XX)	X.XXX
Hours to tolerate oral medication, mean (SD)* (baseline to start of oral ACT)				
DRC	XX/XXX (XX)	XX/XXX (XX)	XX/XXX (XX)	X.XXX
Tanzania	XX/XXX (XX)	XX/XXX (XX)	XX/XXX (XX)	X.XXX
All study sites	XX/XXX (XX)	XX/XXX (XX)	XX/XXX (XX)	X.XXX
Parasite clearance half-life in hours, mean (SD)** (excluding patients with initial count insufficient to estimate half-life)				
DRC	X.X (X.X)	X.X (X.X)	X.X (X.X)	X.XXX
Tanzania	X.X (X.X)	X.X (X.X)	X.X (X.X)	X.XXX
All study sites	X.X (X.X)	X.X (X.X)	X.X (X.X)	X.XXX

*Protocol recommends patients receive a minimum of 3 doses of injectable artesunate before switch to oral ACT. Patients may vary if discharged before 24 hours, died, or referred.

** Parasite dynamics will be affected by patients who are transfused.

STATISTICAL ANALYSIS PLAN
3.5 Safety assessments and tolerability (Incidence of adverse events and serious adverse events by study arms within the first 28 days)

Safety analyses will be based on the whole population that get administered the study drug. That is, the safety and tolerability data will be pooled from all the sites that received the same antimalarial treatment.

The safety and tolerability of 1-STEP AS versus 2-STEP AS will be assessed by comparing the frequency (%) of adverse events and serious adverse events, with particular attention to the variables listed below, which pertain to severe malaria.

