Safety data will be presented in tabular and/or graphical format and summarized descriptively. Any clinically relevant abnormalities or values of potential clinically concern will be described. Patients will be analysed following the intention to treat analysis. All adverse event summaries will refer to treatment emergent adverse events, i.e. adverse events that newly started or increased in intensity after the study drug administration. Adverse events will be graded according to Common Terminology Criteria for Adverse Events (CTCAE). The safety and tolerability summaries will be presented in table 5.

Table 5 Incidence of adverse events within first 28 days by study arm

	1-STEP AS	2-STEP AS	p-value
Number of subjects	XX	XX	
Serious adverse events (SAEs), n/N, (%)	XX	XX	X.XXX
Possible, probable or definite drug related SAEs, n/N, (%)	X/XX (X.X)	X/XX (X.X)	X.XXX
Neurological sequelae at discharge	X/XX (X.X)	X/XX (X.X)	X.XXX
Neurological sequelae at 28	X/XX (X.X)	X/XX (X.X)	X.XXX
Neurological sequelae persisting at end of follow up	X/XX (X.X)	X/XX (X.X)	X.XXX
Grading of adverse events, n/N, (%)	1-2	3-4	1-2
Symptoms			
Impaired consciousness or unrousable coma, n (%)	X/XX (X.X)	X/XX (X.X)	X/XX (X.X)
Prostration, n (%)	X/XX (X.X)	X/XX (X.X)	X/XX (X.X)
Failure to feed and drink without assistance, n (%)			
Multiple convulsions, n (%)			
Deep breathing, respiratory distress, n (%)	X/XX (X.X)	X/XX (X.X)	X/XX (X.X)
Circulatory collapse or shock, systolic BP < 70 mmHg, n (%)	X/XX (X.X)	X/XX (X.X)	X/XX (X.X)
Clinical jaundice plus evidence of other vital organ dysfunction, n (%)	X/XX (X.X)	X/XX (X.X)	X/XX (X.X)
Haemoglobinuria, n (%)	X/XX (X.X)	X/XX (X.X)	X/XX (X.X)
Suspected pulmonary oedema, n (%)	X/XX (X.X)	X/XX (X.X)	X/XX (X.X)

STATISTICAL ANALYSIS PLAN

	X/XX (X.X)	X/XX (X.X)	X/XX (X.X)	X/XX (X.X)	X.XXX
Renal failure (< 20 ml urine per hour) , n (%)	X/XX (X.X)	X/XX (X.X)	X/XX (X.X)	X/XX (X.X)	X.XXX
Spontaneous bleeding/disseminated intravascular coagulation, n (%)	X/XX (X.X)	X/XX (X.X)	X/XX (X.X)	X/XX (X.X)	X.XXX
Several episodes of vomiting in the preceding 24 hrs, n (%)	X/XX (X.X)	X/XX (X.X)	X/XX (X.X)	X/XX (X.X)	X.XXX
Severe pallor with respiratory distress OR HCT<15% OR hb<5.0g/dl, n (%)	X/XX (X.X)	X/XX (X.X)	X/XX (X.X)	X/XX (X.X)	X.XXX
Total	X/XX (X.X)	X/XX (X.X)	X/XX (X.X)	X/XX (X.X)	X.XXX
Laboratory abnormalities					
Creatinine	X/XX (X.X)	X/XX (X.X)	X/XX (X.X)	X/XX (X.X)	X.XXX
Total bilirubin	X/XX (X.X)	X/XX (X.X)	X/XX (X.X)	X/XX (X.X)	X.XXX

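### SAP Table 5 is titled adverse-event incidence but has no row for children with any adverse event, or with any non-serious drug-related one

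*SAP*

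**What the plan says.** SAP 2.1.3 makes this an endpoint: "Incidence of adverse events and serious adverse events by study arms within the first 28 days". SAP 3.5 describes how the two products are to be judged on safety: "assessed by comparing the frequency (%) of adverse events and serious adverse events". The same sentence then sets an emphasis for that comparison: "with particular attention to the variables listed below, which pertain to severe malaria". Further on, the section names the place for the results: "The safety and tolerability summaries will be presented in table 5". No other safety shell is given.

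Two looser provisions stand beside that commitment. One is "Safety data will be presented in tabular and/or graphical format and summarized descriptively". The other is "Any clinically relevant abnormalities or values of potential clinically concern will be described". Neither comes with a layout, a denominator or a selection rule.

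Protocol 8 says that all AEs and SAEs are recorded so that the safety and tolerability of the two formulations can be compared. Protocol 8.1.1 lists common conditions of severe malaria that are not to be reported as AEs when they result from its deterioration; they go in a separate part of the CRF. Protocol 12.4.1 describes the known reactions to the drug: "More common minor side effects described in association with parenteral administration of artesunate include dizziness, light-headedness, rash, and taste alteration", plus a rare severe allergic reaction.

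**The concern.** The two arms give the same active drug, so the safety question specific to this trial is how the new formulation is tolerated. Protocol 6.7 says of the 1-step product: "Each ampoule of 6 ml solvent contains: sodium bicarbonate 8.4mg/ml; arginine 20mg/ml". The 2-step product uses bicarbonate and saline and lists no arginine. Appendix 1 also gives different strengths for the IV solution: 20 mg/ml for 1-step and 10 mg/ml for 2-step. Protocol 3.2 notes that the new product has not yet been used in patients with severe malaria.

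Filled in as drawn, Table 5 would mainly show whether signs of malaria differed between arms. A difference in minor drug reactions would be recorded in the CRF but would enter no comparison that the SAP specifies. A reader could also take *Total*, under a title that promises AE incidence, as the overall AE rate, which it does not appear to be.

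**Working it through.** **The plan's own figure.** The SAP gives no figure for the AE comparison. Its only computed design figure is the sample size, set on preparation time: n per arm = 2(1.960 + 1.282)² × 2² / 1² = 84.1, rounded up to 85; 85 / (1 − 0.15) = 100. It reproduces and is not in question here. It shows that the trial was not sized for AEs.

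**Step 1: what Table 5 contains.** Below the number of subjects there are 2 SAE rows (all; drug-related), 3 neurological-sequelae rows, 13 symptom rows, *Total*, and 7 laboratory rows. Rows for any AE: 0. Rows for any non-serious drug-related AE: 0. Rows for AEs by reported term outside the listed signs: 0.

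**Step 2: where the 13 symptom rows come from.** I set each against baseline Table 1 and against the protocol 8.1.1 list. The matching to 8.1.1 is by clinical concept, because the definitions are not identical (renal failure, for example, has different urine-output limits).

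| Table 5 symptom row (abbreviated) | In Table 1 | Counterpart in 8.1.1 |
|---|---|---|
| Consciousness / coma | yes | yes |
| Prostration | yes | no |
| Failure to feed | yes | no |
| Convulsions | yes | yes |
| Respiratory distress | yes | yes |
| Shock | yes | yes |
| Jaundice | yes | yes |
| Haemoglobinuria | yes | yes |
| Pulmonary oedema | yes | no |
| Renal failure | yes | yes |
| Bleeding / DIC | yes | yes |
| Repeated vomiting | yes | no |
| Severe pallor / anaemia | yes | yes |
| **Count** | **13 of 13** | **9 of 13** |

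The order is also the same as in Table 1. The vomiting row still refers to the preceding 24 hours, which is an admission item and not a 28-day event.

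**Step 3: what *Total* covers.** It follows the 13 signs and comes before the laboratory block. The SAP does not define it. If 8.1.1 is applied, most of what it sums is not AE data and it may be nearly empty. If 8.1.1 is not applied, it counts events that the protocol says are not AEs.

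**Step 4: where the reactions in protocol 12.4.1 would land.**

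| Reaction | Place in Table 5 |
|---|---|
| Any serious reaction | SAE rows, including drug-related SAEs |
| Hypotension, dyspnoea (as allergic symptoms) | Partial overlap with shock and respiratory distress |
| Vomiting | Partial overlap with repeated vomiting |
| Delayed haemolysis | Haematocrit decrease, haemoglobinuria, severe pallor |
| Non-serious rash, urticaria, pruritus | None |
| Dizziness, light-headedness, taste change | None |

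So a non-serious AE that is not one of the 13 signs, the 7 laboratory items or a neurological sequela adds nothing to Table 5.

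**Step 5: which reactions matter in practice.** Protocol 12.4.1 puts severe allergy at about 1 in 3000. The chance of seeing at least one case is 1 − (2999/3000)^100 = 3.3% in 100 children and 1 − (2999/3000)^200 = 6.5% in 200. Such a case would probably be serious and so would have a row. The gap therefore concerns mainly the commoner minor reactions.

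**The case against.** The best defence is that the SAP text already commits to the analysis. It says the frequency of AEs will be compared, and *particular attention* to some variables adds emphasis without restricting the comparison. This stands. A reader might infer from the shell that AE incidence is never to be computed; the documents do not support that. The text plans the comparison and the table does not display it.

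Three other strong readings also fail:

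- *Table 5 is the only safety output.* It is the only shell. However, SAP 3.5 allows other tables or graphs and a description of relevant abnormalities, and protocol 9.2.2 gives a general method for proportions. None of these names an any-AE count, and describing selected abnormalities does not replace an incidence with a denominator.
- *Drug reactions have no row.* Serious ones do, and several signs overlap in part (Step 4). Protocol 12.4.1 also calls the attribution of nausea, vomiting, anorexia and diarrhoea uncertain, and it does not name injection-site reactions. The missing group is non-serious skin, allergic and sensory reactions.
- *Total certainly sums only the 13 signs.* This is inferred from position. The table as read is also damaged around a page break, with a truncated grade header and a line of cells that has no label. What can be said is that *Total* is undefined and sits where it appears to close the symptom block.

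It can also be said that the AE comparison is exploratory in protocol 4.3 and 5.4.3 (though the SAP lists it as secondary), that protocol 3.2 says the study is not powered for it, and that no data are lost because all AEs are recorded. This limits the weight of the point. It does not supply the missing rows.

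**Conclusion.** The point holds as a mismatch between the SAP's stated AE comparison and the one table meant to carry it. All 13 symptom rows are baseline severity signs, about 9 of the 13 correspond to conditions that protocol 8.1.1 sets apart from AEs, and no row gives the incidence of any AE or of any non-serious drug-related AE.

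The conclusion rests on three things: the row count, which is secure; the matching to 8.1.1, which is a judgement on concepts and could move by a row or so; and the reading of *Total* from its position. It does not rest on any expected difference in tolerability between the arms.

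A reader might take this as a threat to the trial's main conclusion. It is not: preparation time, costs and the sample size are untouched. It is still more than missing detail, because the table filled in as drawn would carry the title of AE incidence while reporting mostly something else.

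**What to change.** In SAP Table 5:

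1. Add a row for children with at least one AE of any kind, and a row for children with at least one AE judged possibly, probably or definitely related to study drug. Give n/N by arm with a 95% CI.
2. Add a listing of AEs by reported term and arm, including the reactions named in protocol 12.4.1 (rash, urticaria, pruritus, dizziness, light-headedness, taste change). Injection-site reactions will appear there if reported.
3. Define *Total* or remove it.
4. Move the 13 malaria signs to a separately labelled block. State whether they are counted as AEs, so that the SAP and protocol 8.1.1 agree.

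Cost: a change to the SAP table shell and a slightly longer table. AEs, their relatedness (protocol 8.3.3) and the daily symptom questionnaire are already collected, and protocol 9.2.2 already provides for exact 95% CIs on proportions. No new data and no change in sample size are needed.

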8. SAFETY REPORTING

This trial will use parenteral artesunate followed by an ACT (expected to be artemether-lumefantrine, or other ACT), drugs that are registered and have been evaluated extensively.

To allow for comparison of safety and tolerability of 1-step injectable artesunate compared to conventional injectable artesunate we will record and review all Adverse Events (AEs) and Serious Adverse Events, (SAEs) that occur in the study.

A symptom questionnaire will be performed daily during hospitalization and at each subsequent visit to the health care facility, to aid in the identification of adverse events.

The investigator is responsible for the detection and documentation of events meeting the criteria and definition of an adverse event (AE), or serious adverse event (SAE), as provided in this protocol.

All SAEs, and AEs will be promptly documented from the moment of randomization in the study to discontinuation of the patient from study participation. Any events occurring between screening and randomization will be considered as baseline, pre-existing conditions. Any conditions that were present at baseline will not be considered adverse events unless the grade of the condition deteriorates.

Each adverse event will be graded according Common Terminology Criteria for Adverse Events (CTCAE) version 5.0:

https://ctep.cancer.gov/protocolDevelopment/electronic_applications/ctc.htm#ctc_50

All adverse events must be recorded in the AE /SAE CRF. To avoid colloquial expressions, the adverse event should be reported in standard medical terminology. Whenever possible, the adverse event should be evaluated and reported as a diagnosis rather than as individual signs or symptoms. If a definitive diagnosis is not possible, then the individual symptoms and signs should be recorded. Whenever possible, the aetiology of the abnormal findings will be documented on the CRF. Any additional relevant laboratory results obtained by the Investigator during the course of this study will be recorded on the CRF.

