8.1 Definitions

8.1.1. Adverse Event (AE)

An AE is any undesirable event or clinical deterioration that occurs to a study participant during the course of the study; that is, from the time of administration of study drugs until study ends (i.e., until the follow up visit) whether or not that event is considered related to the study drugs, or to a concomitant drug or procedure, e.g.

- any unfavourable and unintended symptom
- physical sign
- abnormal laboratory result
- an illness
- any pre-existing condition that has worsened in grade

Any new clinical sign or clinical deterioration that occurs between signing the consent form and the administration of study drugs is not an AE. This information will be recorded in the medical records, as a pre-existing condition.

Condition associated with severe malaria

Common conditions resulting from a deterioration of severe malaria as per list should not be considered or reported as Adverse Events. They are recorded in the specific section of the CRF.

A list of the most common conditions in severe malaria includes,

- Deterioration of BCS or GCS
- Coma not present at admission
- Convulsions not present at admission
- Posturing not present at admission
- Decompensated shock (children systolic BP <70 mm Hg)
- Compensated shock (capillary refill >3sec /temperature gradient)
- Respiratory distress
- Hypoglycaemia (glucose <3 mmol/L)
- Severe anaemia
- Severe bleeding (requiring blood transfusion)
- Hemoglobinuria
- Severe jaundice
- Renal failure (urine output <0.5 mL/kg/hr >24 hours)

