8.1.2. Serious Adverse Event

A serious adverse event is an AE that:

- results in death
- is life-threatening i.e. the patient was at risk of death at the time of the AE
- requires inpatient hospitalization or prolongation of existing hospitalization
- results in persistent or significant disability/incapacity
- Any other significant medical condition

More than one of the above criteria can be applicable to the one event. Other significant medical conditions may be considered an SAE when, based upon appropriate medical judgment, they may jeopardize the patient or require medical or surgical intervention to prevent one of the outcomes listed in the definition above.

All AEs must be followed until resolution, or until the AE is deemed permanent or leads to death.

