8.2 Reporting Procedures for Serious Adverse Events (SAEs)/ SUSARs

All SAEs are recorded in a CRF. They need are to be reported as follows:

Safety team:

All SAEs are to be reported to Safety team (PI, Sponsor representative (CTSG), project coordinator, and medical monitor) by e-mail to [contact] within 24 hours of site awareness. If further data is required, additional documentation can be submitted, but an initial report should be submitted within the 24-hour timeframe.

SAE, including death, resulting from a deterioration of severe malaria will not follow expedited reporting (24-hour timeframe), but reported monthly.

DSMB:

All SAEs are reported to DSMB on a monthly basis

Ethics Committee and the Regulatory Authorities:

All SAEs must also be reported to the ECs and the Regulatory Authorities as per required by local guidelines

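### Nine of the 13 symptom rows in SAP Table 5 overlap conditions that protocol 8.1.1 keeps out of AE reporting, so they omit malaria-attributed deteriorations, mainly non-serious ones

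*SAP*

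**What the plan says.** SAP 3.5 compares the frequency of AEs and SAEs by arm, "with particular attention to the variables listed below, which pertain to severe malaria". It adds: "All adverse event summaries will refer to treatment emergent adverse events". Table 5 is titled as an AE incidence table over 28 days, and its 13 symptom rows sit under a heading for graded AEs.

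Protocol 8.1.1 sets a different rule for the same kind of event: "Common conditions resulting from a deterioration of severe malaria as per list should not be considered or reported as Adverse Events". On where such events go, it says: "They are recorded in the specific section of the CRF". Protocol section 8 also says: "Any conditions that were present at baseline will not be considered adverse events unless the grade of the condition deteriorates".

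On serious events the protocol is not consistent. Section 8.1.2 opens its definition with "A serious adverse event is an AE that". Section 8.2 then says: "SAE, including death, resulting from a deterioration of severe malaria will not follow expedited reporting".

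The SAP does not mention the 8.1.1 exclusion. It does not name the separate CRF section as a source for Table 5, and it has no other table for these complications.

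**The concern.** The SAP singles out severe-malaria conditions for comparison, then counts them through a reporting route that the protocol closes to most of them. A child who develops new convulsions or respiratory distress on treatment, judged to be the malaria getting worse, is recorded on the CRF but has no place in the symptom rows.

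Two things are at stake. First, few events in both arms could be read as reassurance when the row was never able to hold the relevant events. This matters because the 1-step product had not yet been deployed in severe malaria (protocol 3.2). Second, whether an event enters the row depends on an attribution made by an investigator who knows the arm (protocol 6.3), so the counts could differ between arms without a true difference.

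AE and SAE incidence is exploratory in the protocol (5.4.3) and listed as secondary in the SAP (2.1.3). The primary endpoints are not involved.

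**Working it through.** **1. Row overlap.** Each symptom row of Table 5 is set against the list in protocol 8.1.1.

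| Table 5 symptom row | 8.1.1 condition |
|---|---|
| Impaired consciousness or coma | Fall in BCS or GCS; new coma |
| Multiple convulsions | New convulsions |
| Respiratory distress | Respiratory distress |
| Shock, systolic BP <70 | Decompensated shock |
| Jaundice with organ dysfunction | Severe jaundice |
| Haemoglobinuria | Haemoglobinuria |
| Renal failure | Renal failure (different threshold) |
| Spontaneous bleeding or DIC | Severe bleeding needing transfusion (narrower) |
| Severe pallor, Hct <15% or Hb <5.0 g/dl | Severe anaemia |
| Prostration | None |
| Failure to feed or drink | None |
| Pulmonary oedema | None |
| Repeated vomiting | None |

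Nine rows overlap and four do not (9 + 4 = 13).

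**2. Where each kind of event goes if both documents are followed.**

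| Post-dose event | Destination |
|---|---|
| Meets 8.1.1, attributed to malaria, not serious | Dedicated CRF section; no SAP table |
| Meets 8.1.1, attributed to malaria, serious or fatal | SAE row under 8.2, although 8.1.2 requires an SAE to be an AE |
| Meets 8.1.1, attributed to another cause | AE; Table 5 symptom row |
| Fits the Table 5 label but falls outside the 8.1.1 definition | Not barred by the list; can reach the symptom row |
| Present at baseline, grade not worse | Not an AE; rightly not counted |

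The gap is the first line, with an ambiguity in the second.

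**3. Renal threshold.** Table 5 has "Renal failure (< 20 ml urine per hour"). Appendix 4 applies that cut-off to adults. Protocol 8.1.1 uses <0.5 mL/kg/h for more than 24 hours. Per-kilogram equivalent = 20 / weight:

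- 5 kg (the minimum weight for entry): 20/5 = 4 mL/kg/h, or 4/0.5 = 8 times the 8.1.1 threshold.
- 10 kg: 20/10 = 2 mL/kg/h, or 4 times.
- 20 kg: 20/20 = 1 mL/kg/h, or 2 times.
- The two rates agree only at 20/0.5 = 40 kg.

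The row therefore cannot simply be filled from the 8.1.1 section as it stands.

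**4. Illustration of size. All rates here are assumptions; the documents give none.** Count shown = 100 per arm × true rate × share classed as AE. Take true rates of 10% and 20% for any listed complication.

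| Share classed as AE | Count shown per 100 |
|---|---|
| 100% (attribution ignored) | 10 vs 20 |
| 50% | 5 vs 10 |
| 25% | 2.5 vs 5 |
| 10% | 1 vs 2 |
| 0% | 0 vs 0 |

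With attribution ignored, the 95% CI half-width is 1.96 × √((0.1×0.9 + 0.2×0.8)/100) = 1.96 × 0.05 = 0.098, or 9.8 percentage points.

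For differential attribution, take equal true rates of 20% and shares of 10% (2-step) and 30% (1-step). The table then shows 100×0.20×0.10 = 2 against 100×0.20×0.30 = 6, Fisher p = 0.28.

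**The case against.** The strongest reply is that the 13 labels repeat the severity signs of SAP Table 1 and are described as severe-malaria variables. The authors may have meant to fill them from the severity section of the CRF. That is possible, and the CRF is not among the documents, so it cannot be excluded. But the SAP text says treatment-emergent AEs, and one sentence naming the source would be needed to make the other reading the plan. The SAP's promise to describe clinically relevant abnormalities permits a tabulation but does not commit to one.

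Three stronger conclusions are tempting, and the documents do not support them.

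- *Malaria deaths disappear from Table 5.* Section 8.2 speaks of SAEs, including death, from malaria deterioration, and has all SAEs recorded in a CRF and reported monthly to the DSMB. Death is not on the 8.1.1 list. The natural reading puts these events in the SAE row, and the wording of 8.1.2 creates an ambiguity rather than a loss.
- *The nine rows can hold only events unrelated to malaria.* This fails for events outside the 8.1.1 definitions, such as urine output under 20 ml/h that is still above 0.5 mL/kg/h, or bleeding that needs no transfusion.
- *The protocol's safeguard against an unexpected difference in drug activity is lost.* In protocol 3.2 that precaution refers to parasite clearance, which SAP Table 4 reports with fever clearance and time to oral treatment.

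It is also fair to say that Table 5 is wider than its symptom rows. Its neurological sequelae rows are not restricted to AEs, and its laboratory rows bear on renal, jaundice and anaemia events. The trial is not powered for safety, which is to be summarised descriptively, so power calculations on assumed rates carry little weight.

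**Conclusion.** The conflict stands and is minor. Followed together, the two documents leave malaria-attributed deteriorations that meet the 8.1.1 definitions out of nine of 13 symptom rows. The missing events are mainly non-serious ones. The row count and the renal arithmetic come directly from the documents. The number of events lost does not: it depends on unknown complication rates and on the share classed as AEs. The direction is fixed, since any share below 100% shrinks the counts. Possible bias from unblinded attribution is a risk, not a demonstrated effect; the 2 vs 6 example is well within chance.

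**What to change.** In SAP 3.5:

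1. Move the nine overlapping rows from Table 5 to a descriptive by-arm table of new or worsening severe-malaria complications after the first study dose.
2. Count it from the dedicated CRF section and the AE form together, regardless of attribution, each child once per condition, with all children given study drug as the denominator. Use the 8.1.1 definitions, including the renal one.
3. Add a row for any listed complication, with a risk difference and 95% CI.
4. State that the SAE row includes deaths and other serious events from malaria deterioration, shown as a sub-row. A matching sentence in protocol 8.1.2 would remove the tension with 8.2.

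A hypoglycaemia row is an optional addition: the condition is on the 8.1.1 list and glucose is already monitored, but Table 5 has no row for it. A weight-based renal cut-off at admission in Table 1 is not proposed, because Appendix 3 schedules no urine-output measurement.

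The cost is SAP wording and one table that takes over existing rows. Protocol 8.1.1 says these conditions are recorded on the CRF, so no new patients or samples are needed. The downsides are a longer descriptive safety section and counts that depend on how completely that CRF section is filled in. Whether it dates events relative to the first dose should be checked first.
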